10 INTERIM ANALYSIS

An interim analysis for safety and overwhelming efficacy will be performed once 50% of patients have 24 hours of follow-up complete. Enrollment will pause once 50% of patients have received treatment and will remain paused until the DSMC makes their recommendation after their safety review. The DSMC will meet one or two days after enrollment is paused to review the safety data collected within the first 24 hours of follow-up on all enrolled patients. We additionally expect blood count labs collected at day 5 to be available in approximately 25% of patients at the time of the DSMC review.

The DSMC will also review the efficacy data on all randomized participants at this meeting. The interim efficacy analysis will use the same methods as are planned for the final analysis using the ITT analysis. Based on the results of the interim analysis, the DSMC will either recommend to the sponsor to terminate the study for overwhelming efficacy ($p < 0.00001$ at the interim analysis),

terminate the study for safety concerns, modify the study, or continue the study as planned. No formal stopping rules for futility are planned.

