
Individual Stopping Rule
	
A subject should be removed from favipiravir treatment if one of the following criteria is met:
 
 • AST or ALT > 8 x ULN • ALT or AST > 3 x ULN AND total bilirubin > 2X ULN • AST or ALT > 3 x ULN AND patient has right upper quadrant pain or eosinophilia

	
 • Uric acid >20mg/dL 
A subject whose treatment is terminated should remain in the study for appropriate follow up assessments.

Study Measurements: Efficacy, Safety and PK
	
Primary Measurement (Efficacy):
 
 1. Time to first of two negative tests based on nasal swab for RT-PCR taken daily from Day 1 to Day 10, and Days 14, 21, and 28. 
Secondary Measurements (Safety, Efficacy and PK):
 
 2. Oropharyngeal swab for nucleic acid (RT-PCR) taken Day 1, 5, 10, and 28. 3. Symptom improvement or worsening: Subjects will fill in a diary daily, recording the following symptoms: 
 a. Cough b. Sore throat c. Headache d. Nasal congestion e. Body aches and pains f. Fatigue g. Oral temperature taken after 4 pm and at least four hours after ingesting the most recent antipyretic (acetaminophen or NSAID) h. Dyspnea i. Shaking chills j. New loss of taste or smell k. GI symptoms including nausea, vomiting, and/or diarrhea l. Chest pain 4. Safety as assessed by: 
 a. Observed and reported adverse events b. Clinical laboratory evaluations of blood on Days 1, 5, 10, and 28 c. Physical Examination at screening (pre-dose Day 1), Days 10, and 28 d. Daily vital signs: pulse oximetry, heart rate, and temperature. 5. Optional Blood for determination of antibodies to SARS-CoV-2 will be obtained on Days 1 and 28. Collection of blood for antibodies is optional for sites. 6. Optional Blood for PK obtained pre-dose (within 30 minutes prior to dosing) and post-dose (45 to 75 minutes following dosing) on Days 1, 5 and 10. Collection of PK is optional for sites. 7. Optional Stool samples for determination of viral load in stool and microbiome characterization will be obtained in the following

	windows Day 1±5, 14±7, and 28±7. Collection of stool is optional for sites.
--	---

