9.2 Sample size justification

Approximately 180 patients will be enrolled.

Assuming 1:1 randomization and the use of a two-sided log rank test at the $\alpha=0.04999$ level of significance for the final analysis, 79 events will provide 80% power to detect a hazard ratio of 2.03. This leaves $\alpha=0.00001$ to check for overwhelming efficacy after 60 participants have completed 24 hours of follow-up. Assuming the control and treatment arm median cessation of shedding is 14 and 7 days, respectively, a two-month accrual period, a two-week follow-up period after randomization of the last patient, and a drop out of 10% in the control arm, it is estimated that the total sample size required to achieve 79 events is 120 (60 patients in each arm). We assume 33% of patients will test negative for SARS-CoV-2 virus by RT-PCR on Day 1, thus the total sample size required to be randomized is 180 ($120/0.67$). The assumption of 33% is based on calculations performed after the DSMB recommended a sample size re-estimation to account for the patients who test negative at baseline and do not contribute meaningfully to the primary analysis.

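### Section 10 names only first-24-hour safety data and Day-5 blood counts for the DSMC, not the on-treatment liver, uric acid and creatinine results that the treatment-removal criteria use, and its 25% figure does not fit two-month accrual

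*Combined protocol and SAP*

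**What the plan says.** **The review.** Section 10 sets the trigger: "An interim analysis for safety and overwhelming efficacy will be performed once 50% of patients have 24 hours of follow-up complete". Enrolment then stops until the DSMC reports, and "The DSMC will meet one or two days after enrollment is paused". Its safety task is to "review the safety data collected within the first 24 hours of follow-up on all enrolled patients". One further item is named: "We additionally expect blood count labs collected at day 5 to be available in approximately 25% of patients". The DSMC may recommend termination for safety.

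**The interim size.** Section 9.2 places the efficacy look "after 60 participants have completed 24 hours of follow-up", while the same section says "Approximately 180 patients will be enrolled". It assumes "a two-month accrual period, a two-week follow-up period after randomization of the last patient".

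**The laboratory schedule.** The synopsis lists "Clinical laboratory evaluations of blood on Days 1, 5, 10, and 28". Section 7.1 puts the Day 1 bloods among the pre-dose procedures, and footnote A to the Section 14 schedule accepts CBC, Chem 7 and LFT results from within 48 hours of enrolment. The Section 14 schedule shows one combined draw (CBC, Chem 7, LFTs, uric acid, CRP) on Days 1, 5, 10 and 28.

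**The removal criteria.** The synopsis and Section 5.3 both use AST/ALT, bilirubin and uric acid. A creatinine clearance limit appears in Section 5.3 only.

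**The concern.** Sections 6.1 and 7.2 define Day 1 as the first 24 hours, so the named safety window covers the loading-dose day of a 10-day course. No clinical laboratory sample is scheduled between the pre-dose sample and Day 5. From the Day-5 draw, Section 10 names the blood counts and leaves out the components that the removal criteria depend on.

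Adverse event listings would not reliably fill the gap. Section 8.6 says that laboratory abnormalities are usually not recorded as AEs unless clinically significant, and Section 2.3 describes the uric acid rises as asymptomatic.

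A data manager could therefore follow Section 10 to the letter and give the DSMC no on-treatment chemistry. A recommendation to resume enrolment would then be read as reassurance about ten days of dosing while resting mainly on the first day. The 25% figure adds to this, because it suggests that little later data would exist when the plan's own accrual implies that most of it would.

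**Working it through.** **Step 1: what the named package contains.**

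| Result | Scheduled in first 24 h, after dosing | Scheduled on Day 5 | Named in Section 10 |
|---|---|---|---|
| Blood counts | No | Yes | Yes |
| AST, ALT, bilirubin | No | Yes, same draw | No |
| Uric acid | No | Yes, same draw | No |
| Creatinine | No | Yes, same draw | No |

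Section 10 sets no such time limit on efficacy and says that the final-analysis methods apply to it. It says nothing comparable for safety, so the by-visit laboratory summaries and shift tables of Section 9.7 are not carried into the interim.

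**Step 2: can the 25% be reproduced?** Inputs: two months taken as 60 days; accrual assumed uniform (the documents give no shape); review r = 1 or 2 days after the pause (Section 10); Day d falls d − 1 days after Day 1. T is the time to enrol the interim cohort:

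- 50% of patients (90 of 180 at 3/day, or 60 of 120 at 2/day): T = 30 days.
- 60 of 180 at 3/day: T = 20 days.

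Share at or past Day d = (T − (d − 1) + r)/T, with a floor of zero.

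| Interim | Time | Day 5 | Day 10 | Day 28 |
|---|---|---|---|---|
| 50% of patients | At pause | 26/30 = 87% | 21/30 = 70% | 3/30 = 10% |
| | 1 day later | 27/30 = 90% | 22/30 = 73% | 4/30 = 13% |
| | 2 days later | 28/30 = 93% | 23/30 = 77% | 5/30 = 17% |
| 60 of 180 | At pause | 16/20 = 80% | 11/20 = 55% | 0% |
| | 1 day later | 17/20 = 85% | 12/20 = 60% | 0% |
| | 2 days later | 18/20 = 90% | 13/20 = 65% | 0% |

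In patients with Day 5 reached at the review, this is 81–84 of 90, 54–56 of 60 (when the total is 120), or 51–54 of 60 (when the total is 180). The 25% is not reproduced as a share of the interim cohort.

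**Step 3: sensitivity.**

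- Visit one day early or late (Section 7.3), plus an assumed laboratory turnaround of 0–1 day, makes the lag 3 to 6 days. Less r, that is 1 to 5 days. T = 30 gives 25/30 to 29/30 = 83–97%; T = 20 gives 15/20 to 19/20 = 75–95%.
- One-month accrual halves T. T = 15 gives 12/15 to 13/15 = 80–87%; T = 10 gives 7/10 to 8/10 = 70–80%.
- Without any assumption on accrual shape: for only 25% to have reached Day 5 by the review, 75% of the cohort must have enrolled in the last 2–3 days before the pause. For 90 patients that is 67.5/3 to 67.5/2, about 22.5–34 per day; for 60 it is 45/3 to 45/2 = 15–22.5 per day. The plan implies 2–3 per day.
- If the 25% is a share of the planned total: 81–84 of 180, or 54–56 of 120, is 45–47%; 51–54 of 180 is 28–30%.

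**Step 4: what the difference is worth.** With zero events in n patients, the one-sided 95% upper bound on the event rate is 1 − 0.05^(1/n).

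- 25% of 90 is about 22, or 11 per arm: bound 24%.
- 25% of 60 is 15, or 7 per arm: bound 35%.
- About 90% of 90 gives 40 per arm: bound 7%.

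**The case against.** The strongest reply is that silence is not exclusion. Section 10 does not say only, and it withholds nothing. Day-5 chemistry comes from the same tube draw as the counts, and blood count labs may be loose wording for the whole draw. A reader might infer that the DSMC is barred from chemistry or would certainly see none. The documents do not support that. What stands is narrower: the text names a window and one laboratory component, and does not call for the rest.

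Four other strong inferences also fail:

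- **That these are trial-level stopping rules resting on chemistry alone.** They are individual removal criteria. One combines AST/ALT with right upper quadrant pain or eosinophilia, so symptoms and the differential count matter too.
- **That the package cannot show the expected harms.** Section 2.3 names diarrhoea with uric acid elevation as the two most common AEs, and diarrhoea could be reported within 24 hours.
- **That participants are unprotected.** Sites apply the removal criteria using the scheduled laboratory visits, AEs are recorded through Day 28 (Section 8.4.1), and SAEs reach the sponsor within 24 hours (Section 8.4.6).
- **That the 25% is impossible on every reading.** As a share of all 180 planned patients with the interim at 60, it would be 28–30%, or 25–32% with visit windows and turnaround, which is close. But Section 10, where the figure stands, sets the interim at 50% of patients and speaks of enrolled patients; on that trigger even the planned-total reading gives 45–47%.

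Two practical objections also carry weight. Section 9 defers full analysis detail to a separate SAP, which may say more. Section 9.2 reports a DSMB recommendation on sample size, so some review has evidently taken place, though not necessarily this one.

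**Conclusion.** The point holds in this form. Section 10 names first-24-hour safety data and Day-5 blood counts, and does not provide for review of the on-treatment liver, uric acid and creatinine results that the individual removal criteria use. This first part rests on the text and the schedule and needs no accrual assumption.

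The second part, on the 25%, assumes uniform accrual over two months and takes the interim cohort as the denominator. The plan then implies 90–93% at Day 5 by the review (interim at 50% of patients) or 85–90% (60 of 180), and 75–97% across both triggers once visit windows and a one-day turnaround are allowed for. Any accrual pattern that gives 25% of the interim cohort would need most of it to enrol within two or three days.

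The matter concerns what the interim safety review can support. It does not bear on the validity of the final efficacy comparison. It should be corrected, since the data are already scheduled for collection.

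**What to change.** In Section 10:

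- State that the DSMC receives all safety data accumulated to the data cut on every randomised participant, by arm: AEs, SAEs, treatment discontinuations, vital signs, haematology, and chemistry including AST, ALT, bilirubin, creatinine/CrCl and uric acid. Give the numbers who have reached Days 5, 10 and 28.
- Keep 24 hours only as the trigger, meaning the minimum follow-up for the last participant in the interim cohort.
- Restate the 25% from actual accrual, and give its denominator.
- Reconcile the interim size: 60 participants in Section 9.2 against 50% of patients in Section 10, which is 90 of 180.

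The synopsis and Section 5.3 should also be reconciled on whether CrCl is a removal criterion.

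The cost is wording, a wider data extract and some data cleaning within the one or two days before the meeting. No visit or sample is added. The documents give no laboratory turnaround or cleaning time, so the most recent results may be incomplete; a stated data cut handles this. If this review has already taken place, apply the rule to any later DSMC review.

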11 RECORDING AND COLLECTION OF DATA

11.1 Case Report Form

The Investigator or designee will record all data collected on the electronic Case Report Form (eCRF) provided for that purpose. For this study, REDCAP cloud will be the eCRF. The site will be suitably trained on the use of the eCRF and appropriate site personnel will be provided electronic signatures.

All site entries will be made in a secured web site and the Principal Investigator will review the record for completeness. Upon completion of the review, the PI will sign electronically in the signature page of the eCRF.

The Investigator or designee will make necessary eCRF corrections. The investigator must authorize the corrections to the entered data on eCRF.

Specific instructions on use of the EDC system and guidelines for data entry and correction will be provided to the sites.

11.2 Study Files and Subject Source Documents

Subject confidentiality is strictly held in trust by the participating investigators, research staff, the Sponsor and their designees. This confidentiality is extended to cover testing of biological samples in addition to the clinical information relating to subjects. Authorized representatives of the Sponsor may inspect all documents and records required to be maintained by the Investigator, including but not limited to, medical records (office, clinic or hospital) and pharmacy records for the subjects in this study. Any data, specimens, forms, reports, and other records that leave the site will be identified only by a subject identification number to maintain confidentiality.

The Investigator must maintain adequate and accurate records to enable the conduct of the study to be fully documented and the study data to be subsequently verified. These documents include Investigators' Study Files and original subject clinical source documents generated at the study site. The term "original" means the first recording of the data.

The Investigator will ensure the site master files are maintained, including the study protocol and its amendments, IRB and regulatory approvals with associated correspondence, informed consents, study drug records, staff curriculum vitae, all correspondence, and other appropriate documents.

Subject clinical source documents may include, but are not limited to, subject hospital/clinic records, physicians' and nurses' notes, appointment books, laboratory reports, ECGs, radiographs, and consultant letters. The Investigator must assure that all original source documents are available to support monitoring activities.

11.3 Monitoring

Due to the restrictions imposed on clinical and hospital visits by the COVID-19 pandemic, most monitoring activities of this study will be conducted remotely. Monitors will work with the site

study staff at each site to determine times for “joint” remote or in-person monitoring – meaning that the monitor and the site study staff will review data together.

Monitoring will be conducted according to the applicable ICH and GCP guidelines to ensure protocol adherence, quality of data, drug accountability, compliance with regulatory requirements and continued adequacy of the investigational site and its facilities. The site study staff will cooperate in the monitoring process by ensuring the availability of the eCRFs, source documents and other necessary documents at the time of monitoring and by prompt attention to any matters brought to their attention by the monitor.

11.4 Audit

ICH guidelines for GCP require independent inspection of clinical program activities. Such inspections may be performed at any time - before, during and/or after the study. The site Investigator and site study staff are responsible for maintaining the site master file containing all study-related regulatory documentation as outlined by the Sponsor that will be suitable for inspection at any time by the Sponsor, its designees, and/or regulatory agencies. The Investigator understands and agrees to give access to the necessary documentation and files.

11.5 Retention of Data

All records connected with this clinical study will be retained for at least two years following the date of an approved marketing application [21 CFR 312.62(c)]; or at least three years from the formal discontinuation of favipiravir development; or seven years from the end of the study, whichever is longer. All local laws regarding retention of records must also be followed. Study sites are required to retain all records until written notification allowing destruction is received from the Sponsor.

12 ETHICS

12.1 Ethics Committee

A properly constituted, valid IRB/IEC must review the treatment plan and procedures, the Investigator’s informed consent document, and related subject information. It is the responsibility of the Investigator to ensure that all aspects of institutional review are conducted in accordance with current regulations governing the jurisdiction where the study is conducted. The Sponsor (or designee) must receive a letter documenting IRB/IEC approval that specifically identifies the title of the treatment plan, subject information sheet, and ICF.

12.2 Subject Information and Consent

It is the responsibility of the site Investigator to ensure that written informed consent is obtained from the subject or legal representative before any activity or procedure is undertaken that is not part of routine care. The informed consent must comply with local regulations.

The background of the study, the procedures, the potential benefits and risks of the treatment, and the fact that treatment is voluntary for the subject must be explained to the subject or legal representative. The subject or representative must be given sufficient time to consider whether to receive compassionate treatment. A copy of the ICF, signed and dated by the subject/representative and the site Investigator (or designee), must be given to the subject/representative. Confirmation of

a subject's informed consent must also be documented in the subject's medical record prior to any treatment with favipiravir.

Each consent form should contain an authorization allowing the Investigator and the Sponsor (or designee) to use and disclose protected health information (PHI) (i.e., subject-identifiable health information) in compliance with local law. The signed consent form will be retained with the treatment records.

13 GENERAL CONSIDERATIONS

13.1 Discontinuation of the Study

The Sponsor reserves the right to discontinue the study at any time for any reason.

13.2 Use of Information and Publication

All information concerning favipiravir, Sponsor operations, patent applications, formulas, manufacturing processes, basic scientific data, formulation, and other information supplied by the Sponsor to the Investigator and not previously published is considered confidential and remains the sole property of the Sponsor. The Investigator agrees to use this information only to treat this patient and will not use it for other purposes without written consent of the Sponsor.

The information obtained in this study will be used by the Sponsor in connection with the continued development and, if approved, commercialization of favipiravir. Thus, Sponsor may disclose such information as required to other clinical Investigators, contractors, and government regulatory agencies.

Publication or other public presentation of results from this study and related information is subject to the provisions of the Clinical Trial Agreement between Sponsor and the Study Site.

14 SCHEDULE OF ASSESSMENTS

Day	Assessment in the study clinic	Administration of study drugs	Self-collected nasal swab and self-assessment)	Oropharyngeal swab	Blood collected by phlebotomy for clinical labs (CBC, Chem 7, LFTs, uric acid, CRP) ^{A, B}	Blood collected by phlebotomy for biobanking/immunology studies ^C	Blood collected by phlebotomy for PK, pre- and post-dose ^C	Urine for pregnancy test (serum if needed)	Stool self-collected using Zymo fecal kit ^C	Collect nasal swabs for antigen testing	Collect nasal swab for molecular testing
1	X	X	X	X	X	X	X	X	Dispense stool kit	X	X
2		X	X								
3		X	X								
4		X	X								
5	X	X	X	X	X		X	X	X	X	X
6		X	X								
7		X	X								
8		X	X								
9		X	X								
10	X	X	X	X	X		X		Dispense two stool kits	X	X
14			X						X		
21			X								
28	X		X	X	X	X			X, Dispense stool kit		

